The randomization scheme will be stratified according to clinical center partnership because

differences among clinical sites typically yield a large amount of variability. Within each partnership

the randomization will be stratified based on BMI (BMI ≤ 25 vs. BMI > 25) and race (African-American
 vs. other).

C. Adherence

Adherence with the study drug, including capsules and inhaled medications, will be assessed during the run-in phase with the use of a medication event monitoring system (MEMS) for the capsules and dosimeter (DOSER, Newmed Corp.) for MDI. We will require all participants to demonstrate adherence with at least 75% of their prescribed inhaled medication and single-blind placebo vitamin D capsules during the run-in phase (at visit 3) in order to remain in the study and undergo baseline measurements. This will select a cohort of participants who are much more likely to be adherent with the remainder of the study, as our experience with other studies has demonstrated.

V.STUDY POPULATION INCLUSION AND EXCLUSION CRITERIA

1	
2	

A. Inclusion criteria for entry

- All participants will meet ALL of the following inclusion criteria:
- 6 1. Males or females age 18 or greater (at visit 0);
 - 2. Physician-diagnosed asthma for at least previous 12 months (at visit 0);
 - 3. Asthma confirmed by: (a) β -agonist reversibility of FEV₁ \geq 12 % following 180 mcg (4 puffs) levalbuterol at visit 1 OR (b) methacholine FEV₁ PC₂₀ \leq 8 mg/ml if not receiving an inhaled corticosteroid or \leq 16 mg/ml if receiving an inhaled corticosteroid at visit 2. Source documentation for PC₂₀ from an AsthmaNet methacholine challenge completed within 6 months of visit 2 will be accepted;
 - 4. Stable asthma controller therapy (inhaled corticosteroid or leukotriene modifier only) dose for past 2 weeks (at visits 0, 1, and 2);
 - 5. FEV₁ \geq 50% of predicted (evaluated at visits 1, 2 and 3);
 - 6. Vitamin D level of less than 30 ng/ml at visit 0;
 - 7. Ability to provide screening and baseline information at visits 0 and 1;
 - 8. Ability and willingness to provide informed consent at visit 0;
 - 9. Experienced no more than one treatment failure in the VIDA run-in or OCS response periods on previous enrollments;
 - 10. For women of childbearing potential: not pregnant, non-lactating, and agree to practice an adequate birth control method (abstinence, single barrier methods or combination barrier and spermicide, or hormonal) for the duration of the study (at visit 0);

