Although the safe tolerable upper intake level for vitamin D was set at 2,000 IU/day in 1997 by the National Academy of Sciences Institute of Medicine for adults and children greater than 1 year of age, (119) recent analyses indicate that this level could safely be updated to 10,000 IU/d, well above our chosen daily dose of 4,000 IU/day (110, 120, 121). As a benchmark, this same (4,000 IU/d) dose has been employed by other investigators in studies in related diseases such as atopic dermatitis (e.g. by the NIAID-funded Atopic Dermatitis and Vaccinia Immunization Network) (122) and an ongoing maternal supplementation study (123).

VIII. POWER ANALYSIS AND STATISTICAL METHODOLOGY

A. Power Analysis

In order to have 90% power to detect a hazard ratio of 1.8 from a Cox regression model (a reduction in treatment failure rate from 40% in the control group to approximately 24-25% in the intervention group during the randomized treatment period), a sample size of 200 participants per group is required. This calculation assumes an overall alpha level of 0.05, a 2-sided test, and 15% withdrawal (Power Analysis and Sample Size (PASS) Software 2008).

B. Statistical analysis methods

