The primary outcome of time from randomization to treatment failure will be evaluated during both the inhaled corticosteroid-stable and inhaled corticosteroid-taper phase of the trial. The pattern of treatment failure in the intervention and control groups will be visually described using the Kaplan-Meier method. The primary analysis will be a Cox proportional hazards regression model with time to treatment failure, from randomization, as the outcome and treatment group as the covariate of primary interest. Because we suspect that the hazard ratios to compare between the two groups may be different between the steroid-stable and steroid-taper phases of the trial, we will include taper status as a participant-specific time-dependent covariate as well as the interaction between taper status and treatment. If there is no clinically significant evidence of a treatment by taper interaction (defined below), then the interaction term will be removed from the model and the primary analysis p-value will correspond to the one-degree-of-freedom test of the treatment group main effect. If there is clinically significant evidence of a treatment by taper interaction, then there will be three Bonferroni adjusted p-values corresponding to the three one-degree-of-freedom contrasts for treatment effect within each level of the taper effect (stable, 50% taper and 75% taper).

The interaction effect will be evaluated by clinical, rather than statistical, significance because there is relatively low power for the standard two-degrees-of-freedom test of interaction. Clinical significance will be assessed by calculating the pair-wise ratios of the treatment effect hazard ratios for the three

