levels of the taper effect, and determining them to be clinically significantly different if the ratio of the hazard ratios does not fall within 0.8 to 1.25 (124). If only one of the three pairwise hazard ratio comparisons is clinically non-significant, then the taper levels corresponding to that comparison will be collapsed and the analysis will proceed as if there were only two taper levels. Under the null hypothesis of no treatment effect in any level of taper, this approach has a type-1 error rate of 5%. Under the alternative hypothesis of no interaction between treatment and taper, and with common treatment effect specified in section VIII.A., this approach has 90% power. Under the partially true alternative hypothesis of no treatment effect within two of the taper levels, but with treatment effect as specified above in the other taper level, this approach has a type-1 error rate no greater than 5% for the null taper levels and power of 84% for the non-null taper level. An adjusted model will be evaluated which will include the factors upon which the randomization was stratified: center, BMI (overweight/obese status), and race (African-American status). A secondary adjusted model will also consider the inclusion of the following baseline covariates that are of potential importance: gender, age, baseline 25(OH)D level, baseline sun exposure, baseline skin pigmentation level, FEV1 % predicted, OCS responsiveness, bronchodilator reversibility, and methacholine responsiveness (PC₂₀) measured on a continuous scale and transformed with the log₂ transformation. We will also evaluate the effect of seasonality on the study results by including season as a time-varying covariate in the adjusted model. The primary analysis will follow the intent-to-treat principle.

1

2

3

4

5

6

7

8

9

10

11

12

13

14

15

16

17

18

19

20

21

22

23

24

25

Vitamin D responder analysis: an exploratory analysis will be performed related to the primary hypothesis which will compare only those participants who reach sufficient levels of 25(OH)D in the treated group (≥30 ng/ml) to those participants in the control group, with respect to time to treatment failure as described above.

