The effect of the intervention on the secondary outcomes will be characterized by the change in each measure during each of the study phases. Repeated measures analysis of variance models (RM-ANOVA) will be fit to the measurements to evaluate the change over time from baseline (Visit 3 – to allow for stabilization of control on 4 weeks of low dose inhaled corticosteroid) to the end of the inhaled corticosteroid-stable phase, as well as the change over time during the inhaled corticosteroid-taper phase. These changes over time will be estimated and compared between the treatment groups with the specification of appropriate contrast statements, and a modified auto-regressive correlation structure will be specified to reflect the longitudinal design. Repeated measures analysis of

covariance models (RM-ANCOVA) will also be fit to the secondary outcomes as discussed above, with potential adjustment for the baseline covariates listed above. The secondary outcome measuring time to exacerbation will be evaluated using survival analysis methods as described for the primary outcome.

The secondary hypothesis to evaluate the effect of the intervention within overweight participants and African Americans will be addressed by fitting RM-ANOVA models to the lung function measures within those participants with BMI ≥ 25 and within African Americans. As described above, the models will compare the change in lung function measurements over the treatment period between the intervention groups. A RM-ANCOVA model will also be fit within each of these subgroups to compare the change in lung function measures between the intervention and control groups with adjustment for the appropriate baseline factors included above. Assuming we will have approximately 50% of randomized participants in the overweight category, and approximately 30-40% African Americans, we will have the following power to detect the following effect sizes to address this secondary hypothesis.

Power estimates assuming an overall alpha=0.05, 2-sided tests, 15% withdrawal, and using change in $FEV_1(L)$ as the lung function measure with standard deviation = 0.375 from the ACRN MIA trial

Subset	Sample size	Power	Effect Size
Overweight/obese	100 per group (50%)	80%	0.16 L
· ·		85%	0.17 L
		90%	0.19 L
African American	80 per group (40%)	80%	0.18 L
		85%	0.19 L
		90%	0.21 L
		80%	0.21 L
	60 per group (30%)	85%	0.23 L
		90%	0.24 L

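### The primary Cox model leaves out the factors used to stratify randomization; adding them would cost nothing and would remove a possible conservatism

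*Protocol*

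**What the plan says.** Protocol IV.B stratifies the allocation by clinical center partnership on the ground that "differences among clinical sites typically yield a large amount of variability". Within each partnership it is further "stratified based on BMI (BMI ≤ 25 vs. BMI > 25", and by race (African-American or other).

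Protocol VIII.B describes the primary analysis as a Cox model with "treatment group as the covariate of primary interest", plus time-dependent taper status and its interaction with treatment. If the interaction is judged not clinically significant and dropped, the primary p-value is the one-degree-of-freedom test of treatment. Otherwise there are Bonferroni-adjusted treatment contrasts by taper level. Center, BMI and race are not among the terms of this model.

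They come later in the same section: "An adjusted model will be evaluated which will include the factors upon which the randomization was stratified". A further model, called secondary, adds other baseline covariates.

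The overweight subgroup analysis in VIII.B is run in "participants with BMI ≥ 25 and within African Americans", which is not the cut used for randomization.

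The sample size in VIII.A is set as follows: "In order to have 90% power to detect a hazard ratio of 1.8 from a Cox regression model", described as "a reduction in treatment failure rate from 40% in the control group to approximately 24-25% in the intervention group". "This calculation assumes an overall alpha level of 0.05, a 2-sided test, and 15% withdrawal". The result is 200 per group.

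**The concern.** The protocol stratifies because it expects sites to differ widely, then leaves site out of the deciding test. Stratified allocation balances the arms on these factors, so the treatment estimate varies less from trial to trial than a model without them assumes. If the factors are prognostic, two things follow. The test rejects less often than 5% under the null. The hazard ratio from the model without the factors is also closer to 1 than the one from the model with them. At stake is efficiency, not validity. Since this is a stated choice of primary model, it is not a detail left to an SAP.

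**Working it through.** **1. The plan's own figure.** Inputs from VIII.A: control failure 40%, hazard ratio 1.8, two-sided 0.05, 90% power, 15% withdrawal, 400 participants.

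- Failure with vitamin D under exponential hazards: 1 − 0.6^(1/1.8) = 24.7%, which agrees with the stated 24-25%.
- Events needed (Schoenfeld): 4(1.960 + 1.282)² / (ln 1.8)² = 42.0 / 0.3455 ≈ 122.
- Hazards over the treatment period: control −ln 0.6 = 0.511; vitamin D 0.511/1.8 = 0.284; withdrawal −ln 0.85 = 0.163, taken as a competing exponential process.
- Expected events: 200 × 0.372 + 200 × 0.229 ≈ 120.
- Power: Φ(√(120.1/4) × 0.588 − 1.960) = Φ(1.26) = 89.6%.

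The stated 90% is reproduced.

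**2. Simulation with the hazard ratio fixed at 1.8 within strata.** There were 2,000 trials per scenario, with 400 participants and 1:1 allocation. From the protocol: overall control failure 40%, 15% withdrawal, 50% overweight, and 35% African American (midpoint of the stated 30-40%). Assumed: nine centers, blocks of 4 within center × BMI × race, and the stratum effects:

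- none;
- weak: SD of center log hazards 0.3, hazard ratio 1.2 each for BMI and race;
- moderate: SD 0.5, hazard ratio 1.5 each;
- strong: SD 0.8, hazard ratio 2.0 each.

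Under the null, treatment-only model:

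| Stratum effects | Mean model SE | Actual SD of log HR | Type-1 error |
|---|---|---|---|
| None | 0.165 | 0.164 | 5.1% |
| Weak | 0.165 | 0.162 | 4.3% |
| Moderate | 0.165 | 0.157 | 3.8% |
| Strong | 0.166 | 0.150 | 3.0% |

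The ratio of model SE to actual SD explains the conservatism. With strong effects it is 0.166/0.150 ≈ 1.10, so the effective critical value is about 1.96 × 1.10 = 2.16, or about 3% two-sided. The adjusted model rejected in 4.9 to 5.4% of null trials.

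Under the alternative:

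| Stratum effects | Power, treatment only | Power, adjusted | Gain (points) |
|---|---|---|---|
| None | 88.8% | 89.1% | 0.3 |
| Weak | 88.7% | 89.4% | 0.7 |
| Moderate | 85.6% | 89.5% | 3.9 |
| Strong | 80.1% | 89.3% | 9.2 |

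In the moderate case the mean SE was 0.188 unadjusted and 0.189 adjusted, so adjusting does not shrink it. What moves is the estimate: log HR −0.563 against −0.605 (moderate), and −0.515 against −0.608 (strong). As control-versus-vitamin-D ratios these are exp(0.563) = 1.76 against exp(0.605) = 1.83, and 1.67 against 1.84.

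A separate simulation (1,500 trials per scenario; center SD 0.3-0.6, race log HR 0.4-0.7, BMI log HR 0.2-0.4) gave 87-89% unadjusted against 90-92% adjusted, and unadjusted type-1 error of 3.7-4.4%.

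**3. Simulation with the overall rates held at 40% and 24.7%** (1,500 trials per scenario):

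| Stratum effects | Power, treatment only | Power, adjusted |
|---|---|---|
| None | 88.2% | 88.6% |
| Weak | 88.9% | 89.7% |
| Moderate | 90.9% | 93.2% |
| Center SD 0.6, race log HR 0.7, BMI log HR 0.4 | 90.3% | 92.9% (at least one adjusted fit did not converge) |

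The gain is about 0.4 to 2.6 points, and the unadjusted test is already near 90%. A smaller run (400 trials per scenario, Monte Carlo error about 1 to 1.5 points) gave the same direction for moderate effects: type-1 error about 3.5% against 5%, and 1 to 2 points of power.

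**4. Stratifying on every cell.** Nine centers × 2 × 2 = 36 cells, which is 400/36 ≈ 11 participants and 120/36 ≈ 3 events each. In the simulation of step 2 this gave 86.7 to 88.1% power, less than covariate adjustment in every scenario.

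**5. BMI cut.** Randomization puts a BMI of exactly 25 in the lower stratum; the subgroup analysis counts it as overweight. Only participants at exactly 25 are affected.

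**The case against.** In favor of the plan, the unadjusted test is valid, errs on the safe side and is clearly designated as primary, and the adjusted analysis is prespecified. All of that stands.

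It can be added that the lower unadjusted hazard ratio is not a bias. Cox hazard ratios are non-collapsible, so the two models estimate different quantities. VIII.A ties 1.8 to overall failure proportions, which are marginal. Fixing 1.8 within strata weakens the overall effect and makes the unadjusted test look underpowered by construction. This also stands, and it is why the 4- and 9-point gains should be read as conditional on that reading of 1.8.

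Three stronger readings are tempting, but the document does not support them.

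- That the stratification is ignored: a model with exactly these factors is planned.
- That two p-values compete for the primary claim: VIII.B says which test is primary.
- That the unadjusted standard error exceeds the adjusted one: it does not (0.188 against 0.189). It is too large only relative to the true sampling variability under stratified allocation.

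What these arguments do not supply is a reason for keeping the factors out. Adjustment lost no power in any scenario, and the protocol itself expects large site differences.

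**Conclusion.** The point holds as an efficiency improvement. If center, BMI and race are prognostic, the planned primary test is conservative, with type-1 error of about 3 to 4.4%, and adjustment recovers power. The gain is about 0 to 3 points for null to moderate effects. It reaches about 4 points (moderate) or 9 (strong) when 1.8 is the within-stratum hazard ratio. With no stratum effects nothing is gained or lost.

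The size is uncertain. The protocol gives no prognostic strength for any of the three factors, and its remark on variability concerns sites only. None of the simulations includes time-dependent taper status or the interaction-selection step. A reader might infer that the trial falls short of its planned power. That does not follow: the stated 90% is reproduced, and it is essentially met without adjustment if the overall rates are 40% and 24-25%. The BMI mismatch is a real but minor inconsistency.

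**What to change.** Make the adjusted analysis primary. To the treatment/taper model in VIII.B add partnership, as a Cox stratum or as a covariate, and the BMI and race randomization strata as covariates. Do not stratify on all center × BMI × race cells. Keep the model without these factors as a sensitivity analysis. If the sponsor prefers the present order, state the reason.

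Define the BMI term by the randomization cut (≤25 against >25) and align the overweight subgroup with it.

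The cost is a sentence or two, made before unblinding. The factors are already recorded for randomization, so no new data or participants are needed.

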If the pre-bronchodilator FEV₁ value at a visit is ≤80% of the pre-bronchodilator value obtained at visit 3, and the participant does not meet other treatment failure criteria, the participant should be given levalbuterol (≥6 puffs in one hour) to assess the degree of reversibility in his/her airflow obstruction. These values must be reported to the physician responsible for the care of the participant on that day. If the physician determines that the participant's response to the bronchodilator is satisfactory, and the participant's clinical condition is stable, the participant may continue in the study, as usual, provided he or she returns to the study site in 24-96 hours for repeat spirometry. In addition, the site coordinator or designee shall telephone the participant every 24 hours to assess his or her condition. No additional provocative procedures (e.g., methacholine challenge, sputum induction) scheduled for that study day should be performed. At the additionally scheduled visit within the next four days, the repeat spirometric pre-bronchodilator FEV₁ value must be >80% of the pre-bronchodilator value obtained at visit 3; if not, the participant will be considered a treatment failure at that time. If spirometric values are within the acceptable range, all procedures for the previously scheduled

- visit shall be performed, and the participant will continue on his/her study medications, as usual.
- Note that this part of the criterion may also be applied at visit 4 (end of OCS response period).
- While unlikely, if the participant meets treatment failure criteria during the OCS response
- 5 period, he or she will be ineligible for randomization at visit 4.
- Note: The FEV₁ criterion will not be applicable during the run-in period (visit 2-visit 3) due to lack of a consistent baseline FEV₁ during that period.
 - 4. Any use of additional inhaled or oral/parenteral corticosteroids related to the treatment of the participant's asthma by the study or treating physician.
 - Need for emergency treatment at a medical facility that is related to, or complicated by, the
 participant's asthma and which results in systemic corticosteroid treatment or hospitalization
 for an acute asthma exacerbation.
 - 6. Participant refusal to continue study drugs because of lack of satisfaction with treatment.
- Physician clinical judgment for safety reasons.

8

9

10

11

12

13

15 16

17

18

19

20

21

22

23

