 - (8) Vitamin D levels. Initial and post-randomization vitamin D levels will be compared to above asthma outcomes. The area under the curve (AUC) for vitamin D levels will be calculated for all individuals and compared to asthma control, quality of life and physiologic measures. In addition, an analysis will be performed restricted to those individuals who achieved sufficient vitamin D levels (>30 ng/ml) during the trial compared to those that did not.
 - (9) Corticosteroid responsiveness. Change in lung function in corticosteroid unresponsive and

- 1 responsive individuals will be evaluated. Corticosteroid-responsive airflow obstruction will be defined
- 2 as a ≥5% improvement in FEV₁ following systemic corticosteroids.
- 3 (10) Total inhaled corticosteroid dose. Cumulative inhaled corticosteroid received dose during all
- 4 study phases (phases I, IIa and IIb) will be calculated and compared to asthma control, quality of life
- 5 and physiologic measures.
- 6 (11) Colds. In all individuals experiencing a cold during the trial, the potential impact of vitamin D
- 7 on respiratory tract infections will be evaluated. The frequency and severity of colds, as reflected by
- 8 the peak Wisconsin Upper Respiratory Symptom Survey-21 (WURSS-21) score (86) during the cold,
- 9 will be compared between those in the vitamin D treatment group to those receiving placebo.
- Secondary analysis of the severity of the cold will evaluate the effect of the intervention on day 1 and
- 11 2 WURSS-21 scores.
- 12 (12) Airway inflammation. Response to vitamin D based on presence of airway inflammation (≥ 3%
- sputum eosinophils) at baseline (visit 3) and change over time in airway inflammation.
- 14 (13) Stress. Levels of perceived stress will be assessed using an adapted version of the Perceived
- 15 Stress Scale (PSS) (87) in all individuals.
- 16 (14) Sinonasal disease. Rhinitis and sinusitis symptoms will be assessed using a Sinonasal
- 17 Questionnaire (SNQ) (88) in all individuals.

IV. PROTOCOL OVERVIEW

A. Protocol design

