Measurement of serum 25(OH) vitamin D - Liaison assay and quality control and blinding considerations. Participants will have peripheral blood collected for vitamin D level at visits 0, 6, 8 and 10. The DiaSorin LIAISON® 250H vitamin D assay is a fully automated system utilizing a direct competitive chemiluminescence immunoassay for the quantitative determination of 25OH vitamin D in serum or plasma. This method has equal specificity to both D2 and D3 forms and provides a total vitamin D result. The DiaSorin LIAISON® 250H vitamin D method is the only fully automated FDA cleared method available today. This assay maintains both inter and intra precision of less than 8% across the linear range. Linearity and recovery, which demonstrate an assay's accuracy, are both excellent with a mean recovery of 102% and an R-squared value for linearity of 0.99. The assay has a measuring range of 4.0 to 150 ng/mL. The results will be expressed in terms of 25-(OH)D and vitamin D insufficiency is defined as level <30 ng/ml. Toxic levels will be considered ≥120 ng/ml (105). Participants above this level will stop blinded study capsules and return to the clinical site for a repeat test as soon as possible. If the second vitamin D level is ≥120 ng/ml, the participant will stay off study capsules for the remainder of the study and will continue to be seen for follow-up visits (intention-totreat). If the repeat vitamin D level is normal, the participant will resume taking study capsules. The LIAISON® 25 OH Vitamin D TOTAL Control Set is used as assayed quality control samples to monitor the accuracy and precision of the DiaSorin LIAISON® 25 OH Vitamin D TOTAL Assay.

1

2

3

4

5

6

7

8

9

10

11

12

13

14

15

16

17

18

19

20

21

22

23

24

25

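### The exploratory vitamin D responder analysis selects on a post-randomisation level in one arm only, so it is not a randomised comparison and would be expected, though not certain, to lean towards vitamin D

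*Protocol*

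**What the plan says.** Section VIII.B introduces the analysis by name and gives its status: "Vitamin D responder analysis: an exploratory analysis will be performed related to the primary hypothesis". It "will compare only those participants who reach sufficient levels of 25(OH)D in the treated group (≥30 ng/ml) to those participants in the control group", using time to treatment failure as already defined in that section. No corresponding selection is made among placebo participants. Just before this, the protocol says: "The primary analysis will follow the intent-to-treat principle".

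Three other places bear on it:

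- **Clock.** Section VIII.B: "The primary outcome of time from randomization to treatment failure will be evaluated". Randomisation is at Visit 4 (study week 5).
- **Levels.** Section VI.D: "Participants will have peripheral blood collected for vitamin D level at visits 0, 6, 8 and 10". Visits 6, 8 and 10 fall at study weeks 17, 25 and 33, which are 12, 20 and 28 weeks after randomisation. Section VI.C adds a sample at the exit visit.
- **Outcome.** Section III.C lists this among the treatment failure criteria: "Participant refusal to continue study drugs because of lack of satisfaction with treatment".

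Section III.D(8) separately plans an analysis "restricted to those individuals who achieved sufficient vitamin D levels (>30 ng/ml) during the trial compared to those that did not". It does not say whether this is within arm or pooled, and it uses a strict inequality where section VIII.B uses at least 30 ng/ml.

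**The concern.** Randomisation makes the whole vitamin D arm comparable with the whole placebo arm. It does not make those vitamin D participants who later reach a threshold comparable with all placebo participants. The placebo arm also contains people who would not have reached 30 ng/ml on vitamin D, and they stay in. If such people fail more often than others, the comparison shows a benefit when vitamin D does nothing.

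The protocol's own definitions give three reasons to expect that direction:

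1. Participants who take few capsules are removed from the vitamin D group, while equally poor adherers on placebo are kept.
2. Refusing study drugs through dissatisfaction counts as a failure, and stopping capsules tends to lower the level. Some failures can therefore remove their own participant from the vitamin D group. No placebo failure is removed this way.
3. Someone who leaves early has fewer scheduled samples at which to qualify, and someone who leaves before Visit 6 without an exit sample has none.

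What is at stake is the reading of a secondary result: a responder hazard ratio shown beside the primary one could be taken as evidence of efficacy when part or all of it is selection.

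**Working it through.** **The plan's own figure.** The protocol gives no figure for the responder analysis. For the primary analysis (section VIII.A: hazard ratio 1.8, 90% power, two-sided 0.05, 40% failure in control, 15% withdrawal), the intervention rate is 1 − 0.6^(1/1.8) = 24.7%, and the Schoenfeld formula needs 122 events. With withdrawal as exponential censoring, 200 per arm yields about 120 events and 89.6% power, and 203 per arm gives 90%. The stated 200 per group is reproduced, so the same setting (200 per arm, 40% failure, 15% withdrawal) is used below. The protocol's 1.8 is control relative to intervention, and that direction is kept.

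**Step 1: bias with no vitamin D effect.** Let w be the share of the vitamin D arm below 30 ng/ml and k their failure hazard relative to reachers. Scale the whole-arm hazard to 1. Reachers then have hazard 1/(1 − w + wk), and placebo has 1, so

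control/responder HR = 1 − w + wk.

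This equals 1 if w = 0 or k = 1, exceeds 1 (favours vitamin D) if k > 1, and is below 1 if k < 1.

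**Step 2: plausible w.** The protocol does not estimate w. Its text supports a range:

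- Section VII.B expects 40-100 ng/mL in all participants, so w = 0.
- Section VII.B also reports that 2 of 30 people in a cited single-dose 100,000 IU study never reached 30 ng/mL: 2/30 = 7%.
- A cited trial of 4,000 IU/day (no loading dose mentioned) gave a mean of 45 ng/ml. With an assumed normal distribution and SD of 10, 12 or 15, P(<30) = Φ((30 − 45)/SD) = 7%, 11% or 16%.

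**Step 3: put in the numbers** (k = 1.5 to 2 is an assumption):

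- w = 0.07: 1 − 0.07 + 0.07 × 1.5 = 1.035; with k = 2, 1.07.
- w = 0.16: 1 − 0.16 + 0.16 × 1.5 = 1.08; with k = 2, 1.16.

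The range is about 1.04 to 1.16. On the log scale, ln 1.035/ln 1.8 = 6% and ln 1.16/ln 1.8 = 25% of the design effect.

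**Step 4: simulation check.** Log-rank tests, 6,000 runs per setting, no vitamin D effect, responders against all placebo. The nominal chance of a significant result favouring vitamin D is 2.5%.

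| Not reaching 30 | k | HR by formula | HR simulated | Significant for vitamin D |
|---|---|---|---|---|
| 5% | 2 | 1.05 | 1.04 | 4.4% |
| 10% | 1.5 | 1.05 | 1.05 | 4.2% |
| 10% | 2 | 1.10 | 1.08 | 6.6% |
| 20% | 1.5 | 1.10 | 1.09 | 7.3% |
| 20% | 2 | 1.20 | 1.17 | 13.8% |
| 20% | 0.67 | 0.93 | 0.93 | 0.8% |
| 5-20% | 1 | 1.00 | 1.00 | 2.1-2.4% |

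The 20% rows lie outside the 7-16% range and only show how the bias grows. The simulation treats reaching the threshold as a fixed trait, so it leaves out the route by which a refusal lowers the level.

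**The case against.** The case for leaving the plan alone is substantial. The analysis is labelled exploratory and the primary analysis is by intention to treat. The protocol expects every treated participant to reach at least 40 ng/mL, in which case nobody is excluded and the responder result equals the primary one. The run-in requires 75% adherence, which removes some of the poor adherers before randomisation. The adjusted models in section VIII.B already list baseline 25(OH)D, pigmentation, BMI and race. All of this limits the size. None of it makes the comparison randomised, and baseline adjustment does not remove selection by later adherence or by the outcome itself.

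A reader might infer more than the protocol supports:

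- **That the bias certainly favours vitamin D.** This needs non-reachers to be at higher risk, which the protocol does not quantify. At lower risk the bias reverses, as the table shows.
- **That heavier or darker-skinned participants are the ones removed.** Section VII.B reports that BMI and body fat did not significantly influence response in one cited study, and that the rise was consistent across ethnic groups in another.
- **That many failures precede the first level.** Section X.D expects most failures during the taper. A failure does not end follow-up either: withdrawal follows the third event (section X.G). The timing problem is therefore mainly one of early leavers.
- **That section III.D(8) is a rival version of this analysis that mixes the arms.** It is a separate item among the secondary outcomes and does not mention arm. Only the missing statement about arms and the differing inequality can be held against it.

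**Conclusion.** The point holds. As written, the responder analysis is a non-randomised comparison created by post-randomisation selection in one arm. A lean towards vitamin D is the reasonable expectation, not a certainty.

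The size rests on two quantities that the protocol does not give: the share staying below 30 ng/ml and their relative hazard. At zero excluded there is no bias. At 7-16% excluded with an assumed 1.5-2 times the hazard, the control/responder hazard ratio under no effect is about 1.04-1.16. This could not by itself produce the design hazard ratio of 1.8, but it is enough to colour a null or borderline result. The primary conclusion is unaffected. The analysis differs from the primary one only when people are excluded, which is when it can mislead, so a correction is worth making.

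**What to change.** 1. Replace the responder analysis with, or report beside it, a complier-type estimate that keeps both randomised arms: the intention-to-treat difference in risk of failure by 28 weeks after randomisation, divided by the between-arm difference in the proportion reaching at least 30 ng/ml. With no effect of assignment, its numerator is centred on zero.
2. State its assumption: assignment acts on failure only through reaching the threshold. A rise that stays below 30 ng/ml could still have an effect, which would violate this. A level first reached after a failure also needs a stated rule.
3. State how participants with no post-randomisation level are handled.
4. If a subset comparison is still shown, adjust it for baseline covariates and label it non-randomised. A landmark start at Visit 6 may be a sensitivity analysis only. It leaves out Phase I and, for first failures, conditions on having come through it, so it does not restore randomisation.
5. In section III.D(8), say whether achievers and non-achievers are compared within arm or pooled, and use one threshold there and in section VIII.B.

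**Cost.** A few lines of text and analysis, with no new data. The interval widens. Treating the denominator as known and assuming no placebo participant reaches 30 ng/ml, it is 1/0.93 = 1.08 to 1/0.84 = 1.19 times as wide as that of the intention-to-treat risk difference when 7-16% of the vitamin D arm fall short. It is wider still if some placebo participants reach the threshold.
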